8.3 Planned degree of statistical significance

Except for the interim analyses described in chapter 8.1.3, a p value <0.05 will be considered as significant for all analyses.

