1.9 Independent Data and Safety Monitoring Board

An independent Data and Safety Monitoring Board will be constituted at the beginning of the study with 5 members who are not involved in the study, including an intensivist, an anesthesiologist, a cardiac surgeon, an infectiologist, a methodologist/statistician.

In order to prematurely stop the study in case of efficacy, two interim analyses are planned. These analyses will be performed on the primary endpoint but will also evaluate safety data in order to rapidly detect any unexpected serious adverse events.

The Data and Safety Monitoring Board will meet after each interim analysis and at the end of the study. It can also meet on request of the coordinating investigator or the methodologist if serious adverse events or results which can jeopardize the existence of the protocol occur.

The Data and Safety Monitoring Board will propose to stop the study if the interim statistical analyses reach significance or if it appears that study continuation would be contrary to ethics rules (occurrence of serious adverse events, publication of trial results providing the answer to the question...).

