8.1 Description of planned statistical methods, including schedule of planned interim analysis

8.1.1Descriptive analysis

A first overall descriptive analysis and analysis by group will be performed. This consists of separate estimates, numbers and percentages for qualitative variables, means, standard error, medians and interquartile intervals for quantitative variables. The normal feature of the distribution of quantitative variables will be checked (Shapiro test).

8.1.2Comparison of groups at inclusion

Student's t test or a Mann-Whitney test if necessary will be used to compare quantitative variables, and a Chi² or Fisher's exact test if necessary will be used to compare qualitative variables between two groups at inclusion.

8.1.3Analysis of the primary criteria

The primary endpoint (rate of nosocomial infection at day-28 after CPB) will be compared between the two groups with the Chi²test.

Two interim analyses after inclusion of 1/3 and 2/3 of the patients, and one final analysis are planned. Stopping rules will use the alpha spending function with the O'Brien-Fleming boundary. The cumulative values of alpha for each analysis are: 0.00021 at the first analysis, 0.01202 at the second analysis and 0.04626 at the final analysis (nTerim, V1.1, Statistical solutions Ltd, Cork, Ireland). The trial will be stopped early if the significance of the Chi² test is below these alpha values.

8.1.4Analysis of other criteria

For the analysis of the other endpoints, the same strategy as for baseline comparisons will be used.

In addition, censored endpoints (survival) will be compared using the log-rank test.

Continuous endpoints repeatedly measured during the study will be compared using a repeated measure two-way (time, group) analysis of variance.

For all these analyses, adjustments can be made in case of heterogeneity at inclusion.

8.1.5Analysis of adverse events

Possible adverse events are coded according to the MedDRA classification and are the patient of a descriptive analysis.

8.2 Planned number of persons to be enrolled in the study, and planned number of persons in each centre with its statistical justification

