Our hypothesis is that 15% of the patients without MV during CPB (MV- group) will have post-operative infection at day 28. A total sample size of 1392 patients (696 per group) is required to achieve 80% power to detect a decrease in the rate of postoperative infection in patients with MV during CPB (MV+ group) to 10%, using a two-sided test with a type I error of 5% (nTerim, V4.0, Statistical solutions Ltd, Cork, Ireland), **1400 will be included to take into account potential non evaluable patients (death during surgery, lost to follow-up...).**

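### Section 8.3 leaves the final primary test at p<0.05, while Section 8.1.3 gives it 0.04626 and mislabels its thresholds as cumulative alpha

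*Combined protocol and SAP*

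**What the plan says.** Section 8.1.3 compares the 28-day infection rate between groups with a Chi² test and sets the schedule: "Two interim analyses after inclusion of 1/3 and 2/3 of the patients, and one final analysis are planned". It names an alpha spending function with the O'Brien-Fleming boundary and continues: "The cumulative values of alpha for each analysis are: 0.00021 at the first analysis, 0.01202 at the second analysis and 0.04626", the last value being for the final analysis. Its only decision rule is "The trial will be stopped early if the significance of the Chi² test is below these alpha values".

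Section 8.3 then sets the general level: "Except for the interim analyses described in chapter 8.1.3, a p value <0.05 will be considered as significant for all analyses".

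Section 1.9 uses the word interim in the same way, for two looks that do not include the final one: "In order to prematurely stop the study in case of efficacy, two interim analyses are planned". Section 7.2.3 does too.

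Section 8.2 assumes 15% infections without ventilation and 10% with it, and an overall two-sided type I error of 5%. It states: "A total sample size of 1392 patients (696 per group) is required to achieve 80% power".

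**The concern.** There are two defects, of unequal weight.

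1. **The final threshold.** In the protocol's own vocabulary the final analysis is not an interim analysis, so the exemption in 8.3 does not reach it and 0.05 applies. Section 8.1.3 assigns it 0.04626. The decision sentence in 8.1.3 does not settle the matter, because it concerns early stopping and a final analysis cannot stop a trial early. No sentence says at what p value the final primary result is significant. A final p between 0.04626 and 0.05 would be a positive trial under one section and a negative trial under the other, and the choice could be made after the result is known. Taking 0.05 after two efficacy looks also exceeds the type I error promised in 8.2.

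2. **The label.** The three values are called cumulative alpha. If they were, the last would have to equal the total alpha of 0.05. They are instead per-look p-value thresholds.

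**Working it through.** **Inputs.** Looks at 1/3, 2/3 and all of the information, O'Brien-Fleming-type spending, and values 0.00021, 0.01202 and 0.04626 (8.1.3). Overall two-sided alpha 0.05, rates 15% and 10%, power 80%, 696 per group (8.2). Final level 0.05 (8.3, read literally).

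**Step 1: reproduce the plan's alpha values.** Spending 0.025 on each side, the cumulative two-sided alpha at information fraction t is

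α(t) = 4·[1 − Φ(z₀.₉₈₇₅/√t)], with z₀.₉₈₇₅ = 2.2414.

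Solving for the boundary at each look by recursive numerical integration gives:

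| Look | Cumulative alpha spent | Boundary Z | Nominal two-sided p | Plan's value |
|---|---|---|---|---|
| 1/3 | 0.00021 | 3.710 | 0.00021 | 0.00021 |
| 2/3 | 0.0121 | 2.511 | 0.01202 | 0.01202 |
| 1 | 0.0500 | 1.993 | 0.04626 | 0.04626 |

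The plan's figures match the nominal column exactly. They are correct thresholds under the wrong name; only at the first look do the two columns coincide.

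**Step 2: overall type I error.** The interim thresholds stay at 0.00021 and 0.01202, and only the final one varies.

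| Final threshold | Cumulative alpha after looks 1, 2, 3 |
|---|---|
| 0.04626 (8.1.3) | 0.00021, 0.01209, 0.0500 |
| 0.05 (8.3, literal) | 0.00021, 0.01209, 0.0535 |

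The excess is 5.35 − 5.00 = 0.35 percentage points. A simulation of 2,000,000 trials with the uncorrected Chi² test at 232, 464 and 696 per group agrees: 5.35% versus 5.00% with both arms at 12.5%, and 5.37% versus 5.03% with both arms at 15%.

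**Step 3: which threshold lies behind the sample size.** With pooled variance,

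n per group = θ²·2p̄(1 − p̄)/δ², where p̄ = 0.125 and δ = 0.05, so n = θ² × 0.21875/0.0025 = 87.5·θ².

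Here θ is the drift that gives 80% power with the stated boundaries.

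- Final 0.04626: θ = 2.8194, n = 87.5 × 7.949 = 695.6, rounded up to 696. This is the plan's figure.
- Final 0.05: θ = 2.7879, n = 87.5 × 7.772 = 680.1, rounded up to 681.
- Fixed design without interim looks: 686.8, rounded up to 687.

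Only 0.04626 reproduces 696. Power at 696 per group is 80.0% with 0.04626 and 80.9% with 0.05.

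**Step 4: a result on which the sections disagree.** Take 104/696 (14.9%) versus 79/696 (11.4%). The pooled rate is 183/1392 = 0.1315, and Z = (25/696)/√(0.1315 × 0.8685 × 2/696) = 1.983. So Chi² = 3.93 and p = 0.0474, which is significant under 8.3 and not under 8.1.3.

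**Step 5: what the label would mean if taken at its word.** If the values were truly cumulative alpha, the total would be 0.04626, the final nominal threshold about 0.0423, and power at 696 per group about 79.0%. The text can thus be read to give three final thresholds: 0.05, 0.04626 and about 0.0423.

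**The case against.** The strongest reply is that the intent is plain. Section 8.1.3 describes one three-look scheme and gives a value for the final look. That value has no purpose unless it governs the final Chi² test, and a specific rule would ordinarily prevail over a general sentence. On this reading 8.3 means to exempt the whole scheme. This is very probably what the authors meant, and Step 3 supports it. But 8.3 does not say so, and the sample-size argument is an inference: 8.2 mentions neither 0.04626 nor an allowance for interim looks. The rule for the primary claim should not have to be reconstructed.

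The effect is also small, and this stands. The two readings give different verdicts in about 0.35% of trials under the null and about 0.87% under 15% versus 10% (80.89% − 80.03%, rounded from unrounded powers). The interim stopping rules and the secondary analyses are not affected.

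The label has no operational effect as long as p is compared directly with the listed values, as 8.1.3 does. That stands too; it is a correction of terms.

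Finally, 0.04626 gives exactly 5% only if the looks fall at 1/3 and 2/3. With all three thresholds fixed, illustrative looks at 30% and 60% give 5.09%, and looks at 40% and 75% give 4.88%. This is a fair caution for the wording of the correction. It does not support 0.05 at the final look.

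**Conclusion.** The concern holds. As written, 8.3 sets a final threshold for the primary endpoint that contradicts 8.1.3, does not fit the sample size in 8.2, and raises the overall two-sided type I error from 5.00% to 5.35%. The consequence is confined to a final p between 0.04626 and 0.05, but there it decides whether the trial is positive. The cumulative label in 8.1.3 is wrong for the second and third values and harmless in use. The plan's numbers themselves are right. These results assume looks at exactly 1/3 and 2/3 of the information and the uncorrected Chi² test; the sample-size match also assumes pooled variance. This should be fixed, and it does not call the design into question.

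**What to change.** - **Section 8.3:** exempt both the interim and the final analyses of the primary endpoint, refer to 8.1.3 for their thresholds, and keep 0.05 for the remaining analyses.
- **Section 8.1.3:** call 0.00021, 0.01202 and 0.04626 nominal two-sided p-value thresholds. Give the cumulative alpha spent beside them (0.00021, 0.0121, 0.0500). State that the final primary result is significant only if p<0.04626.
- **Same section, one further clause:** 0.04626 applies with looks at 1/3 and 2/3; if the actual timing differs, the thresholds are recomputed from the same spending function.

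The cost is a few sentences of wording, which should be settled before any unblinded result is seen. The sample size stays at 696 per group. Compared with a final test at 0.05, power is 80.0% instead of 80.9%, which is the 80% the trial was planned for.

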8.4 Method of management of missing, unused or invalid data

Missing data will not be replaced. Mixed models can be used in analysis of repeated data.

8.5 Choice of persons to include in the analysis

This trial is an intention to treat study, that is all randomized and evaluated patients will be analysed.

9 **RIGHT OF ACCESS TO DATA AND SOURCE DOCUMENTS**

9.1 Access to data

In compliance with GCP:

- the sponsor is in charge of obtaining the agreement of all parties involved in the study to ensure direct access to all sites of study conduct, source data, source documents and reports with the aim of quality control and of an audit by the sponsor,
- investigators will make available to persons in charge of monitoring, of quality control or audit of the study documents and individual data which are strictly necessary for such checking, in compliance with legislative and regulatory conditions in force (articles L.1121-3 and R.5121-13 of the French public health code).

9.2 Source documents

Source data defined as all documents or original items which make it possible to demonstrate the existence or accuracy of data or of a finding recorded in the clinical study will be kept for 15 years by the investigator or by the hospital if it involves a hospital medical dossier.

Source documents consist of a medical dossier, originals of laboratory test results, imaging examination reports, etc.

9.3 Confidentiality of data

In compliance with conditions concerning confidentiality of data to which persons in charge of quality control of the biomedical study have access (article L.1121-3 of the French public health code), in compliance with conditions pertaining to confidentiality of information in particular concerning the type of investigational medicinal products, the tests, persons who are Patients in the study and results obtained (article R. 5121-13 of the French public health code), persons having direct access will take all necessary precautions with the aim of ensuring confidentiality of information pertaining to the investigational medicinal products, tests, the persons who are patients in the study and in particular concerning their identity as well as that of results obtained.

These persons, in the same capacity as the investigators themselves, are patient to professional secrecy (according to conditions defined by articles 226-13 and 226-14 of the French penal code).

During the study or at its end, data collected on persons who are patients in the study and forwarded to the sponsor by the investigators (or all other specialised participants) will be made anonymous (deletion of Patients' names).

They must not in any event clearly reveal the names of the persons concerned or their address.

Only the first letter of the surname and of the first name of the patient are recorded, together with the code number specific for the study indicating the order of inclusion of patients.

The sponsor will make certain that each person who is a patient in the study has provided his or her written agreement for access to his/her personal individual data and strictly necessary for quality control of the study.

10 QUALITY CONTROL AND ASSURANCE

A Clinical Research Associate (CRA) designated by the sponsor will ensure proper conduct of the study and the quality of data collected, in agreement with the Standard Operating Procedures applied in the CHU of Rennes and in compliance with Good Clinical Practice as well as legislative and regulatory conditions in force.

The investigator and members of his team agree to make themselves available at Quality Control visits carried out at regular intervals by the Clinical Research Associate. At these visits the following items will be reviewed:

- informed consent,
- compliance with study protocol and procedures defined in it,
- quality of data collected in the case report forms: accuracy, missing data, consistency of data with "source" documents (medical dossiers, appointment diaries, originals of laboratory test results, etc.).

In addition, the investigators agree to be audited by the sponsor as well as inspected by the competent authorities. All data, all documents and reports can be subject to audits and regulatory inspections without being opposed by medical secrecy.

11 ETHICAL CONSIDERATIONS

11.1 Regulatory and institutional review

The protocol, information form and certificate of consent of the study will be submitted to the relevant independent ethics committee (IEC) for review.

Notification of a favourable opinion from the IEC will be transmitted to the sponsor of the study and to the competent authority. An application for authorisation will be sent by the sponsor to local regulatory authority prior to start of study.

11.2 Substantial changes

In case of a substantial change made to the study protocol by the investigator, it will be approved by the sponsor. The latter must obtain prior to start of study a favourable opinion from the ethics committee and authorisation from the relevant health authority in the setting of their respective competence. Additional consent from persons participating in the study will be collected if necessary.

11.3 Information for patients and written informed consent form

Patients will be completely and truly informed in terms which are understandable to them of the objectives and constraints of the study, the possible risks incurred, measures of supervision and safety necessary, of their right to refuse to participate in the study or of the possibility of retracting their agreement at any time.

All this information is contained in an information and consent form given to the patient. Free, informed and written consent from the patient will be collected by the investigator, or a doctor representing him prior to final inclusion in the study. A copy of the information and consent form signed by both parties will be given to the patient; the investigator will keep the original of it.

11.4 Compensation of patients

None.

11.5 Registration in the national file of persons who are patients in research involving the human person None.

12 DATA PROCESSING AND RETENTION OF DOCUMENTS AND DATA

12.1 Case report forms and data entry

All information required by the study protocol must be recorded in the case report forms and an explanation must be provided for any missing data. Data must be collected progressively as obtained and recorded explicitly in the case report forms.

An electronic case report form (e-CRF) will be made available and data entry will be completed in centres through a WEB interface (Clinsight software, Ennov, Paris (75), France). It solely requires an internet connection and a browser. An aid document for use of this tool will be provided to investigators. The interface between the CRA and the investigator thus will be promoted, making possible the collection and control of data at a distance. Tests of control of consistency of data will be incorporated in electronic format. An audit function is incorporated in the e-CRF thus making it possible to follow any change in study data. This function also makes it possible to clearly identify the person who made a change as well as the date. A justification possibly can be incorporated in comment.

If requested, a paper copy will be printed at the end of the study, authenticated (dated and signed) by the investigator and a copy will be sent to the sponsor and archived.

Data analysis will be carried out by statisticians of the Biostatistics Unit Department of Pharmacology of Rennes.

12.2 CNIL

This study falls within the scope of the "Methodology of Reference" (MR-001) established by the Commission Nationale Informatique et Liberté (CNIL). The CHU of Rennes, sponsor of the study, has signed an agreement of compliance with this "Methodology of Reference".

12.3 Archiving

The following documents will be kept in the respective departments until the end of the period of practical utility. These documents are:

- The study protocol and its Appendixes, and possible amendments,
- The original signed informed information and consent forms,
- Individual data (authenticated copies of raw data),
- Monitoring documents,
- Statistical analyses,

- The study final report.

At the end of the period of practical utility, the documents will be archived by the sponsor for at least 15 years after the end of the study or its early discontinuation, in compliance with institutional practices.

Archived documents cannot be moved or destroyed without agreement of the sponsor. All data, all documents and reports can be subject to an audit or inspection.

13 INSURANCE

The sponsor will take out, for the duration of the study, insurance covering the sponsors civil responsibility as well as that of all doctors involved in conduct of the study. They will also insure the total compensation of all harmful consequences of the study for persons who are Patients in it and their heirs, except when evidence is provided that the harm is not causally related to a fault of the sponsor or that of any participant, without it being possible to oppose the intervention of a third party or the voluntary withdrawal of a person who had initially consented to be participated in the study.

14 STUDY FEASIBILITY

Two smaller scale studies (pilot studies) have been already conducted to test the plan and method of this research study with convincing results (Appendixes 4-5-6).

Eligibility criteria and study design will not hinder enrollment expectations. With 7 centers (almost 10 000 CPB/years) enrollment goals will be achieved.

There are no known open competing studies registered to *clinicaltrials.gov* (September 2016).

Study plan does not conflict with currently accepted practice.

Study has been found to be of great scientific interest among potential co-investigators in surgery, anesthesiology and intensivist.

This study has been endorsed by the REVA network (Appendix 8).

15 RULES PERTAINING TO PUBLICATION

Scientific presentations and reports corresponding to the study will be written under the responsibility of the coordinating investigator of the study with the agreement of the responsible investigators.

First author: [name]

Last author: [name]

The co-authors of the report and of publications will be the investigators and clinicians involved (cardiac surgeon and anaesthesiologist), on a pro rata basis of their contribution in the study, as well as the biostatistician and associated researchers.

Rules on publication will follow international recommendations (N Engl J Med, 1997; 336:309-315).

The study will be recorded on a freely accessible website (Clinical Trials) prior to inclusion of the first patient in the study.

16 LIST OF APPENDIX

Appendix 1: List of investigators

Appendix 2: References to the scientific literature

Appendix 3: Lettre d'information et formulaire de consentement

Appendix 4: Nitric Oxide cardiac surgery

Appendix 5: Mechanical ventilation immunological effects

Appendix 6: CPB induced lymphopenia

Appendix 7: CDC Infections criteria

Appendix 8: Endorsement REVA
